73 study investigators and secured daily in a locked cabinet, along with locked study file box, in the EM APD-R office.

74
75

Assessment	Visit / Follow Up (F/U) Interval Times					
	Initial Presentation	0 min (patient drinks oral solution and starts inhalations)	q10 min until 30 min	1 hour	Hourly until 5 hours	Disposition decision made by patient's attending physician
Study period/interval						
Screening	x					
Informed Consent, discuss Plan, etc.	x					
Allocation according to pre-generated simple randomization sequence	x					
Demographics, History of Present Illness	x					
Medication use	x					
Preparation pad provided		x				
Additional preparation pad offered if needed (up to 10)			x	x	x	
Oral solution provided		x				
Provider contacted for consideration of rescue anti-emetic if vomiting or if subject requests			x	x	x	
Nausea Vomiting VAS		x	x	x	x	x
Episodes of Vomiting		x	x	x	x	x
Pain VAS		x	x	x	x	x
Use of Antiemetic Medication		x	x	x	x	x
Type/Doses of fluids/medications		x	x	x	x	x
Clinical impression						x
Overall Satisfaction VAS						x
Pt perception of pad contents						x
Pt perception of oral solution contents						x
Provider perception of pad contents						x
Provider perception of oral solution contents						x
Investigator perception of pad contents						x
Investigator perception of oral solution contents						x
Summary of adverse events						x

76
77
78
79
30
31

This study concludes at the time of disposition and patient satisfaction will be solicited regardless of outcome.

7.3.1 Collection of Human Biological Specimens. Not applicable.

7.3.1.1 Laboratory evaluations and special precautions. Not applicable.

32
33 **7.3.1.2 Specimen storage.** Not applicable.
34

35 **7.3.2 Data Collection.**

- 36 -Times of subject arrival to ED, bed arrival, study medication receipt (gathered prospectively from order sheet or Essentris)
37 -Patient initial nausea as measured by screening VNRS (0-10): self-reported by the subject.
38 -Demographics: Age in years, sex, FMP/SSN, DOB will be recorded on the study key. Age in years and sex will also be
39 reported on the case report form (CRF). This information will be obtained from the patient's ED medical record labels.
40 -The patient's estimated height, weight, race, smoking history, alcohol use will be recorded on the CRF as self-reported by the
41 patient.
42 -History of Present Illness- Nausea and/or vomiting symptoms of timing, duration, severity, provocation and palliation along

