43 with any other symptoms (i.e. pain) will be recorded on the CRF. This information will be self-reported by the subject.
44 -Pertinent Personal Medical/Surgical History will be recorded on the CRF. This information will be self-reported by the
45 subject.
46 -Current medications, supplements being taken and any allergies will be recorded on the CRF.
47 -Level of nausea, episodes of vomiting, pain level, adverse events, use of antiemetic medication at the 0, 10, 20, 30, and 60
48 minutes, then hourly up to 5 hours and finally at the time of patient disposition will be recorded on the CRF. Satisfaction level
49 will be recorded at study conclusion (time of patient disposition) on a VAS. This information will be self-reported by the
50 subject.
51 -Numbers of episodes of vomiting (discrete episodes separated by 120 seconds) will be recorded on the CRF as reported by
52 the patient or the patient's treating nurse.
53 -Time and doses for all drugs and fluids administered in the ED will be recorded on the CRF.
54 -Clinical impression at the time of patient disposition decision will be recorded on the CRF.
55 -Time of patient disposition decision made by attending physician will be recorded on the CRF.
56 -Any adverse events will be recorded on the CRF.
57 -Patient, provider, and study investigator perceptions of pad and oral solution contents will be recorded on the CRF.

58
59 **7.3.3. Human Biological Specimens/Tissue/Data Banking.** Not applicable.
60

61 **7.4 Statistical Consideration**

62
63 **7.4.1 Sample Size Estimation.**

64 **We expect the standard deviation of the change in baseline to 30 minute VAS scores to be approximately 28.7.¹⁷ We**
65 **define a clinically significant difference as 20 mm on the VAS.¹⁸ Given alpha = 0.025 (reflecting a Bonferonni**
66 **correction for testing of two hypotheses) and beta = 0.2 with two-tailed testing, we estimate we will require 40**
67 **patients per arm.**
68

Estimate Required Sample Size	120
Estimate Participant Drop Out / Withdrawal	60
Total Enrollment Requirement	180

69

Enrollment at Each Site	
SAMMC	180

70
71 **7.4.2 Primary (i.e., primary outcome variables) and secondary endpoints.** Primary outcome is nausea VAS measurement
72 at 30 minutes. Secondary outcomes include nausea VAS measurement at study disposition (the time at which the patient
73 leaves the ED), receipt of rescue anti-emetics, time to disposition, and patient satisfaction.
74

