75 **7.4.3 Data analysis.** In this study, the primary outcome will be evaluated using a two-tailed independent sample student t test.
76 The primary outcome will further be evaluated using a multiple regression model. For secondary outcomes, scale data will be
77 compared using a two-tailed independent sample student t test while categorical data will be compared using a chi-squared
78 test.
79

80 **7.7 Confidentiality.**

31 Protection of Data. Subjects will be assigned a study number upon enrollment in order to facilitate subsequent removal of
32 identifiers upon completion of data analysis. The study number will be recorded on the data collection form and on a study
33 key, which links the study number with the subject's name, FMP, SSN, and DOB. Otherwise patients will be de-identified by
34 eliminating names and collecting only demographic (with ages greater than 89 categorized as "greater than 89"), general
35 description of chief complaint, personal medical, surgical, and medication history; and any other information specific to
36 inclusion and exclusion criteria. The case report forms, signed consent forms, and signed HIPAA authorizations will be stored
37 in a locked cabinet only accessible to the study investigators within the secure EM APD-R office.

38
39 **7.7.1 Certificate of Confidentiality.** N/A.

40 41 **8.0 RISKS/BENEFITS ASSESSMENT**

42
43 **8.1 Risks.** There is a risk to the subjects related to loss of confidentiality. However, this risk is minimized by using a
44 unique study code while collecting study data and limiting access to subject records to the study team. Since all patients
45 will be receiving treatment for nausea (either inhaled isopropyl alcohol, oral ondansetron, or both), we believe the risks of
46 delay in treatment or symptom relief are minimal. Nevertheless, if the treatment to which subjects are allocated is not
47 effective in treating their symptoms, they may experience a delay in rescue therapy and so a delay in symptom relief. We
48 seek to minimize this risk by permitting, subjects to request an antiemetic at any time and to withdraw from the study at
49 any time.

50
51 Additionally, there may be an extremely rare incident of a subject that may have a sensitivity to inhaling ISO. The
52 exclusion criteria were defined to minimize the risks of such reactions by excluding patients recently exposed to
53 medications such as cefoperazone, disulfiram, or metronidazole.

54

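### Section 7.4.3 analyses the primary outcome by t test and by an unspecified regression without naming which decides; a regression on arm and time-0 VAS should be the single deciding analysis.

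*Combined protocol and SAP*

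**What the plan says.** Section 7.4.2 makes the 30-minute nausea VAS the primary outcome. Section 7.4.3 gives it two analyses: "the primary outcome will be evaluated using a two-tailed independent sample student t test", followed by "The primary outcome will further be evaluated using a multiple regression model". For the regression it gives no covariates, model form, alpha or role. Neither analysis is called primary, supportive or a sensitivity analysis, and there is no rule for the case where they disagree. No other section settles this.

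Section 7.4.1 splits alpha over hypotheses only: "Given alpha = 0.025 (reflecting a Bonferonni" and, continuing, "correction for testing of two hypotheses) and beta = 0.2 with two-tailed testing, we estimate we will require 40" patients per arm. Its variability figure is for change, not for the 30-minute score: "We expect the standard deviation of the change in baseline to 30 minute VAS scores to be approximately 28.7". The target difference is 20 mm.

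Only one of the two hypotheses is written out (section 6): ISO plus oral placebo against inhaled saline plus oral ondansetron. Sections 7.3 and 7.3.2 collect nausea VAS at time 0.

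**The concern.** There are two gaps.

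- **The deciding analysis is not named.** The Bonferroni split to 0.025 allows one test per hypothesis. With a second analysis of the same outcome and no stated role for it, a borderline trial could give two answers with no rule for choosing. The regression could also draw on many collected variables, among them age, sex, weight, smoking, medical history, screening VNRS, and time-0 nausea and pain. If the significant analysis were the one reported, the 5% bound over both hypotheses would no longer be secured.
- **The apparent lead analysis ignores baseline.** An unadjusted t test of the 30-minute VAS makes no use of the time-0 score, although the trial was sized on the SD of the change from baseline. Allocation is by simple randomization (section 7.3 table: "Allocation according to pre-generated simple randomization sequence"), so baseline nausea is balanced only by chance. Precision that costs nothing to obtain is left unused.

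**Working it through.** **Inputs from the plan.** Two-sided alpha 0.025 per hypothesis, power 0.80, difference 20 mm, SD 28.7 mm, 40 per arm, three arms.

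**Assumptions, not in the plan.**
- The correlation r between time-0 and 30-minute VAS is 0 to 0.7.
- The second hypothesis is arm 1 (ISO plus ondansetron) against arm 3 (saline plus ondansetron).
- For power, 28.7 mm is the SD of the 30-minute score.

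**1. The plan's sample size.** n = 2 × [28.7 × (2.2414 + 0.8416) / 20]² = 39.15, rounded up to 40 per arm. This reproduces the stated figure. It is the formula for comparing two means at 0.025, with no covariate term. The exact t-based power at 40 per arm is 79.5%.

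**2. Error rate if either analysis could win.** This was simulated under no treatment effect: 40 per arm, normal scores, two comparisons sharing arm 3, and a t test or a baseline-adjusted regression, each at two-sided 0.025.

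| Assumed r | Per hypothesis (planned 2.5%) | Over both (planned at most 5%) |
|---|---|---|
| 0 | 2.8% | 5.1% |
| 0.3 | 3.3% | 6.0% |
| 0.5 | 3.8% | 6.8% |
| 0.7 | 4.4% | 8.0% |

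The t test alone gives 2.5% per hypothesis and about 4.7% over both. A separate run of 100,000 trials per setting gave 2.7%, 3.2%, 4.0% and 4.2% per hypothesis and 5.1%, 6.0%, 7.1% and 7.8% over both. The two analyses share data, so the rates stay below the bound for independent tests: 1 − 0.975² = 4.9% per hypothesis and 1 − 0.975⁴ = 9.6% over both.

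**3. Power with baseline adjustment.** Adjustment reduces the SD to 28.7 × √(1 − r²). Approximate power is Φ(20 / (SD × √(2/40)) − 2.2414).

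| r | Residual SD (mm) | Power, normal formula | Power, simulated |
|---|---|---|---|
| t test | 28.7 | 80.9% | about 80% |
| 0.3 | 27.4 | 84.7% | 83% |
| 0.5 | 24.9 | 91.3% | 90% |
| 0.7 | 20.5 | 98.3% | 98% |

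At r = 0 the regression loses one degree of freedom and less than one point of power (79.5% to 78.9%).

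**4. Sensitivity to what 28.7 describes.** Suppose 28.7 is the SD of change, as section 7.4.1 says, and the variance is the same at both times. The SD of the 30-minute score is then 28.7 / √(2(1 − r)), which is 24.3, 28.7 and 37.1 mm for r = 0.3, 0.5 and 0.7. By the formula in step 3, the t test has 93%, 81% and 57% power. The regression, with residual SDs of 23.1, 24.9 and 26.5 mm, has 95%, 91% and 87%. The regression has the higher power at each of these correlations.

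**5. If both analyses were meant to count.** Splitting again to 0.0125 needs 2 × [28.7 × (2.4977 + 0.8416) / 20]² = 45.9, so 46 per arm or 138 evaluable. Power at 40 per arm would be 73%.

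**The case against.** The strongest reply is that the text already implies an order. The t test comes first, the regression is introduced with the word *further*, the t test is the only two-tailed test named for this outcome, and the sample size is that of a two-group comparison. On that reading, error is 2.5% per hypothesis and below 5% over both. This stands as the more natural reading. It does not amount to pre-specification, because both sentences describe evaluation of the primary outcome and neither analysis is labelled.

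A reader might infer that the plan gives each hypothesis two chances at 0.025. The documents do not support that, since nowhere do they say that success on either analysis counts. The rates in step 2 are conditional on such a rule, and at r = 0 the excess almost vanishes.

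A reader might also treat disagreement between the two analyses as evidence of false positives. When a true effect exists, most disagreement arises because the adjusted model has more power. It shows that a rule is needed, not that alpha is inflated.

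It may also be said that making the regression decisive is a preference, and that labelling it supportive would close the error-rate gap. That is correct for error control alone. The reason to go further is the precision gained from data already collected.

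**Conclusion.** The concern holds in limited form. Section 7.4.3 does not name the deciding analysis or the regression's covariates, and the analysis that appears to lead ignores the time-0 score. Inflation is a conditional risk: 2.8% to 4.4% per hypothesis and 5.1% to 8.0% over both, only if success on either analysis were accepted. It rests on the assumed correlation range and on the assumed second comparison. The power gain at 20 mm, from about 80% to 83%, 90% or 98% for r = 0.3, 0.5 or 0.7, rests on taking 28.7 mm as the SD of the 30-minute score. The sample size is not in error. This should be corrected, but it is not fatal to the trial.

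**What to change.** In section 7.4.3, before unblinding, state the following: *The single deciding analysis of each of the two hypotheses is a linear regression of the 30-minute nausea VAS on treatment arm and time-0 VAS, with no other covariates, tested two-sided at 0.025. The unadjusted t test is supportive and does not determine success.*

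Write out the second hypothesis in the same place. Say also that the time-0 score is the one recorded before the oral solution, because section 7.3 starts the clock at first inhalation, after the solution has been swallowed.

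The cost is a few sentences, with no new data and no more patients. It holds the error rate at 0.025 per hypothesis and leaves 40 per arm in place. What is given up is the freedom to choose between two p-values and, if baseline proves uninformative, less than one point of power.

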14.0 STUDY CLOSURE PROCEDURES. Upon study completion, all data collection forms and the study key will be destroyed. The ICDs and HIPAA authorizations will be stored within the EM APD-R Residency office for three and six years after completion of the study, respectively. A protocol closure form will be submitted.
